Title: A RCT Evaluating Efficacy of Type-I Collagen Skin Substitute vs. Human Amnion Membrane in Treatment of Venous Leg Ulcers

NCT No: NCT06831760

Date: July 8, 2025

Introduction:

Venous leg ulcers (VLUs) are the most common type of chronic lower extremity ulcerations, accounting for 60-80% of all leg ulcers [1]. They affect approximately 0.18% to 1.35% of the general population and impose a substantial economic burden on healthcare systems worldwide [2]. Chronic venous insufficiency leads to sustained hypertension in the venous system, resulting in capillary damage and impaired healing [3]. These ulcers present a significant public health challenge, leading to impaired quality of life, substantial healthcare expenditures, and recurrence rates exceeding 70% [4]. Standard treatments include compression therapy and conventional wound dressings; however, healing rates remain suboptimal, often resulting in prolonged healing times and high recurrence rates [5].

The pathophysiology of venous leg ulcers involves complex interactions between venous hypertension, inflammatory processes, and impaired cellular function within the wound environment. [6] Chronic venous insufficiency leads to increased hydrostatic pressure, capillary leakage, and tissue hypoxia, creating a hostile microenvironment that impedes normal wound healing processes. [7, 8]. The presence of elevated matrix metalloproteinases, chronic inflammation, and bacterial colonization further contributes to delayed healing and wound chronicity. [9]

Wound healing is a complex biological process involving phases of inflammation, proliferation, and remodelling. Traditional wound care often fails to adequately stimulate this cascade in chronic wounds, necessitating the use of advanced biologic dressings. [10]

Recent advances in wound care have led to the development of bioengineered skin substitutes designed to address the underlying molecular and cellular deficits in chronic wounds. [11]

Advanced wound care options such as collagen-based dressings and allografts have been developed to enhance the wound healing microenvironment. Among these, Type-I collagen-based skin substitutes (HPTC) (such as *Helicoll®*) and dehydrated human amnion/chorion membrane (dHACM) have gained prominence [12-15].

HPTC is a high purity Type-I collagen matrix derived from bovine tendon and processed to preserve native triple-helix structure, providing a biocompatible scaffold for cellular ingrowth and promote angiogenesis [16]. dHACM comprises preserved amniotic tissue layers, rich in cytokines and growth factors, and extracellular matrix components that theoretically promote wound healing through regenerative mechanisms. Clinical studies have demonstrated the efficacy of dHACM in various chronic wound types [17].

Recent systematic reviews indicate that bioengineered skin substitutes may improve healing outcomes in venous leg ulcers, with healing probabilities ranging from 0.11 to 0.65 over variable time periods. Clinical trials with dHACM have demonstrated healing rates of 75% at 12 weeks in venous leg ulcers [18-20].

Prior studies in diabetic foot ulcers have reported promising results using HPTC compared to dHACM [21, 22]. While numerous studies have evaluated treatments individually, direct comparative studies evaluating their relative efficacy in venous leg ulcer management is null. The present study aims to bridge this gap by conducting a randomized, controlled clinical trial comparing the efficacy of HPTC and dHACM in terms of healing efficacy and patient-reported outcomes.

Materials and Methods:

This single-centre, prospective, randomized, open label, single-blinded, controlled, parallel-group clinical trial was conducted at a tertiary care centre over a 6-month period. The study protocol was reviewed and approved by the Adichunchanagiri Institute of Medical Sciences Institutional Ethics Committee with approval number AIMS/IEC/004/2025 and conducted in accordance with the Declaration of Helsinki. All participants provided written informed consent before enrolment. Additionally, all study products used in this study were manufactured, handled, and stored in accordance with applicable Good Manufacturing Practices. The study was registered in Clinical Trials.gov with identity number NCT06831760. Confidentiality was maintained with all patient records.

Sixty patients aged 18–80 years with non-infected chronic venous ulcers of more than 4 weeks' duration, measuring between 2 cm² and 25 cm², with adequate arterial inflow (Ankle Brachial Index > 0.8) and willingness to comply with follow-up were included. Exclusion criteria included active infection requiring systemic antibiotics, uncontrolled diabetes, peripheral arterial disease, autoimmune disorders, malignancy, immunosuppression, pregnancy and known allergies to bovine or human-derived products. Patients were randomly allocated into two equal groups using a computer-generated sequence:

- Group A: Treated with High Purity Type-1 collagen-based skin substitute (HPTC) (n=30)
- Group B: Treated with dHACM (n=30)

Intervention: Application protocols followed manufacturer instructions. Wounds were debrided before initial grafting. All patients received standard wound cleaning and compression therapy. In addition:

- Group A received application of HPTC, a high-purity Type-I collagen dressing. The product was sized to cover the entire wound surface with a 1-cm margin and secured with appropriate secondary dressings
- Group B received dHACM graft. The membrane was rehydrated and applied to cover the wound bed completely
- Standard Wound Care for Both Groups - First layer of a non-adherent and porous paraffin gauze followed by Second layer of absorbent gauze pads and then third layer of a soft roll and crepe bandage.

Infection control measures were taken and patient education regarding wound care and leg elevation were given. Repeat application was done if deemed necessary.

Outcome Measures:

Primary Outcome Measure:

- i. Percentage wound area reduction - percentage wound area reduction from week 1 through week 6 plus 1 week follow up measured manually with digital photography

Secondary Outcome Measure:

- i. **Infiltration of vascularity in the ulcer bed** - Infiltration of vascularity in the ulcer bed on day 5 of application. Vascularity assessment will be done using biopsy on Day 0 of application to be compared with Day 5 after application of Type-I Collagen-based Skin Substitute or Human Amnion/Chorion Membrane. [Time Frame: 6 days]. Histopathological Assessment – Before application and on the 5th day post-application of either HPTC or dHCAM, a 2mm punch biopsy was obtained from the wound edge extending into the wound bed under local anaesthesia (2% lidocaine without epinephrine). Biopsy samples were immediately fixed in 10% neutral buffered formalin for 24 hours, processed through graded alcohols, and embedded in paraffin blocks. Serial sections of 4 μ m thickness were prepared and stained with:
 - i. Hematoxylin and Eosin (H&E) for general morphology
 - ii. Masson's Trichrome for collagen assessment
 - iii. CD31 immunohistochemistry for capillary density evaluation
 - iv. α -SMA immunohistochemistry for fibroblast activity

Histological Parameters Evaluated

1. Vascular Infiltration: Assessed by counting new blood vessels per High Power Field (hpf) **(0-3 scale)**
 - 0: Minimal vascular ingrowth (<5 vessels/hpf)
 - 1: Mild infiltration (5-10 vessels/hpf)
 - 2: Moderate infiltration (11-20 vessels/hpf)
 - 3: Abundant infiltration (>20 vessels/hpf)
2. Neo-epithelialization: Measured as epithelial migration distance from wound edge **(0-3 scale)**
 - 0: No epithelial migration
 - 1: Minimal migration (<25% wound coverage)
 - 2: Moderate migration (25-75% coverage)
 - 3: Extensive migration (>75% coverage)

3. Fibroblast Activity: Quantified by counting α -SMA positive fibroblasts per HPF and assessment of fibroblast morphology (**0-3 scale**)
 - 0: Sparse, inactive fibroblasts
 - 1: Moderate cellularity, minimal matrix production
 - 2: High cellularity, active-matrix synthesis
 - 3: Very high activity with extensive matrix deposition
4. Capillary Density: Evaluated using CD31 staining, counted as vessels per mm^2 of tissue
5. Inflammatory Response: Graded semi-quantitatively (**0-3 scale**)
 - 0: Minimal inflammatory infiltrate
 - 1: Mild chronic inflammation
 - 2: Moderate mixed inflammation
 - 3: Severe acute inflammation
6. Collagen Deposition: Assessed using Masson's Trichrome staining (**0-3 scale**)
 - 0: Minimal collagen matrix
 - 1: Loose, immature collagen
 - 2: Moderate organized collagen
 - 3: Dense, mature collagen architecture

All histological assessments were performed by two independent pathologists blinded to treatment allocation. Inter-observer agreement was assessed using Cohen's kappa coefficient.

- ii. Time to achieve complete wound closure - the time to achieve complete wound closure (defined as 100% epithelialization with no drainage) of the target ulcer by the end of 6 weeks [Time Frame: 6 weeks]
- iii. Proportion of subjects to obtain complete closure - the proportion of subjects that obtain complete closure over the 6-week treatment period [Time Frame: 6 Weeks]
- iv. Mean number of repeated application - mean number of repeated applications of the Advanced Skin Substitute & Human Amnion/Chorion Membrane used to obtain wound closure [Time Frame: 6 Weeks]
- v. Incidence of adverse events - incidence of adverse events related to the intervention (e.g., infection, allergic reactions) [Time Frame: 6 Weeks]

Other Pre-specified Outcome Measures:

- i. Change in Pain - change in pain measured by a Visual Analog Scale with score range from 0 to 10, wherein 0="no pain" to 10="severe pain" [Time Frame: 7 weeks including 1-week follow-up]. Pain scores were assessed weekly.
- ii. Change in quality of life - change in quality of life assessed using the Wound-QoL questionnaire measured as 'not at all', 'a little', 'moderately', 'quite a lot' and 'very much' for 17 questions [Time Frame: 7 weeks including 1-week follow-up]
- iii. Healed Wound appearance assessment using Manchester Scar Scale - the resultant new skin is assessed and documented at each visit using the Manchester Scar Scale assessing colour, finish, contour, distortion & texture with values given from 1 to 4 wherein 1 denotes excellent and 4 means poor [Time Frame: 7 weeks including 1-week follow-up]

Data Collection and Monitoring

- a. Baseline data: Demographics, medical history, ulcer characteristics.
- b. Weekly follow-ups: Wound measurements (photographic documentation), assess healing progress, pain scores, record adverse events and patient-reported outcomes.
- c. Histopathological specimens were obtained at baseline and day 5 for vascularity assessment.
- d. End-of-Study Visit (Week 6): final wound assessment, collect patient feedback on treatment experience, quality of life and scar assessment.
- e. Data entry and monitoring was managed using an electronic data capture system.

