- e. Data entry and monitoring was managed using an electronic data capture system.

Data Analysis: Data was analysed using SPSS v26.0. Continuous variables were expressed as mean \pm standard deviation, and categorical variables as frequencies and percentages. Student's t-test was used for comparing continuous variables between groups, and chi-square test for categorical variables. A p-value <0.05 was considered statistically significant. Kaplan-Meier survival analysis was used to assess time to complete healing and Cohen's d values for primary histopathological parameters.

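### Secondary outcome i gives the Day 0 biopsy no stated role in the analysis; define it as the between-arm Day 5 difference adjusted for Day 0

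*Protocol*

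**What the plan says.** In the protocol, item i under Secondary Outcome Measure opens with "Infiltration of vascularity in the ulcer bed on day 5 of application", which is a single-time-point outcome. The next sentence makes it a before-after outcome: "Vascularity assessment will be done using biopsy on Day 0 of application to be compared with Day 5 after application" of one product or the other. Neither sentence says that the comparison is between arms. The histology text in the same item says that, before application and again on the fifth day, "a 2mm punch biopsy was obtained from the wound edge extending into the wound bed under local anaesthesia". Vascularity is recorded in two forms: vessels per high-power field, banded 0 to 3, and CD31 capillary density per square millimetre.

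The Intervention paragraph applies to both arms: "Wounds were debrided before initial grafting", and "All patients received standard wound cleaning and compression therapy". On allocation, the protocol says: "Patients were randomly allocated into two equal groups using a computer-generated sequence". Both groups, 30 patients each, receive an active product.

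The SAP's Data Analysis section says "Student's t-test was used for comparing continuous variables between groups" and gives chi-square for categorical variables. It names no paired test, change score or baseline covariate. It adds Cohen's d for the main histology parameters without saying which contrast d describes.

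Three details are not stated: whether debridement comes before or after the Day 0 punch, when compression starts relative to Day 0, and whether the Day 5 punch is taken away from the first site.

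**The concern.** The outcome has two readings (Day 5 level, or Day 0 to Day 5 change) and the SAP chooses neither. Every patient has two biopsies, but the planned tests say nothing about how the first is used. Two things are at stake.

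- **Interpretation.** The Introduction already describes HPTC as promoting angiogenesis. With Cohen's d left open, a before-after d within the HPTC arm could be reported and read as confirmation. Such a rise could come partly or wholly from care that both arms share.
- **Precision.** If the between-group test is run on Day 5 values alone, the information in the Day 0 biopsy is discarded. If it is run on raw change scores, noise from the Day 0 biopsy is added whenever the two biopsies correlate weakly.

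**Working it through.** **The plan's own figure.** The documents give no mean, SD, correlation or power for vascularity. The only design figure is the SAP's sample size for healing rate: (1.96 + 0.84)² × [0.6 × 0.4 + 0.9 × 0.1] / 0.3² = 7.84 × 0.33 / 0.09 = 28.75. This agrees with the stated 28.8, about 29 per group, but has no bearing on this outcome.

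**Step 1: does shared care bias the comparison?** A simulation of 20,000 trials used 30 patients per arm, normally distributed Day 0 to Day 5 changes with SD 1, no product effect, and the same assumed shift in both arms. The share of trials with p < 0.05 was:

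| Shared shift (SD) | Within one arm, Day 0 vs Day 5 | Between arms |
|---|---|---|
| 0 | 5% | 4.8% |
| 0.25 | 27% | 5.2% |
| 0.5 | 75% | 4.9% |
| 0.75 | 98% | 5.0% |
| 1.0 | 99.9% | 4.7% |

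The between-arm test keeps its level. A within-arm test, which the SAP does not name, would not. The shifts are assumptions.

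**Step 2: what is the Day 0 value worth?** Let r be the correlation between a patient's Day 0 and Day 5 values, the same in both arms, and let the Day 0 and Day 5 variances be equal. Relative to Day 5 alone, the variance of the between-arm difference is:

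- Day 5 alone: 1
- change score: 2(1 − r)
- Day 5 adjusted for Day 0: 1 − r²

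Hence Day 5 alone / adjusted = 1/(1 − r²), and change / adjusted = 2(1 − r)/(1 − r²) = 2/(1 + r).

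| r (assumed) | Day 5 alone | Change | Adjusted | Day 5 / adjusted | Change / adjusted |
|---|---|---|---|---|---|
| 0.2 | 1.00 | 1.60 | 0.96 | 1.04 | 1.67 |
| 0.3 | 1.00 | 1.40 | 0.91 | 1.10 | 1.54 |
| 0.5 | 1.00 | 1.00 | 0.75 | 1.33 | 1.33 |

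So 60 patients analysed with adjustment match a Day 5 t-test in 60 × 1.04 ≈ 62 patients at r = 0.2, and 60 × 1.33 ≈ 80 at r = 0.5. The equal-variance assumption matters only for the change-score columns; the ratio 1/(1 − r²) does not need it.

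**Step 3: cost of the extra coefficient.** Chance imbalance in one covariate inflates the variance by about 1 + 1/(60 − 4) = 1.018, or roughly 2%. The net gain over Day 5 alone is then 1.042/1.018 = 1.02 at r = 0.2, 1.099/1.018 = 1.08 at r = 0.3, and 1.333/1.018 = 1.31 at r = 0.5.

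**Step 4: the same in effect-size terms.** With 30 per arm, a two-sided 5% t-test has 80% power for a difference of 0.736 SD. Multiplying by √(1 − r²), before the cost in Step 3, gives 0.736 × 0.980 = 0.72 at r = 0.2 and 0.736 × 0.866 = 0.64 at r = 0.5.

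**The case against.** The strongest defence is that this is a head-to-head trial. The aim is HPTC against dHACM, allocation is randomised, the only named tests are between groups, and the opening sentence of the outcome already names Day 5. Debridement, compression and both biopsies are specified for both arms and cancel in the contrast. No document plans an efficacy conclusion from a within-arm change. All of this stands.

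A reader might go further and infer that the outcome cannot be attributed at all, because debridement, compression and a fresh punch wound fall between the two biopsies and there is no untreated arm. The documents do not support that. An untreated arm is not needed to compare two products. The order of debridement and the Day 0 punch is not given, nor is the start of compression. Any repair response to them is a reasonable inference of unknown size, not a documented fact.

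A reader might also take 33% to 67% as the size of the loss. That range applies only if raw change scores are analysed, and no section specifies them. Against the Day 5 t-test the gain is smaller, and at weak correlation it is slight.

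The defence does not settle which of the two wordings is the outcome, what the Day 0 biopsy is for, or which contrast Cohen's d describes.

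**Conclusion.** The point holds as an unclear outcome definition together with an inexpensive gain in precision. It is not a bias in the randomised comparison. A within-arm rise from Day 0 to Day 5 cannot be credited to either product, and the text leaves room to report one.

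The unadjusted Day 5 t-test gives up the equivalent of about 4% to 33% more patients for r from 0.2 to 0.5, or about 2% to 31% net of the extra coefficient. Raw change scores, if they were used, would give up 33% to 67%. Both ranges rest on an assumed correlation, and the second also on equal variances at Day 0 and Day 5. The direction against change scores holds for every r below 1. Against Day 5 alone, adjustment roughly breaks even near r = 0.13, where 1/(1 − 0.13²) = 1.017, close to the 1.018 cost.

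**What to change.** In the protocol's outcome text and the SAP's Data Analysis section:

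1. Define outcome i as the HPTC minus dHACM difference at Day 5, adjusted for the patient's own Day 0 value. Use a linear model for capillary density and vessel counts. For the 0 to 3 scales, use an ordinal model with the Day 0 score as covariate, since chi-square uses neither the ordering nor the Day 0 score.
2. Base Cohen's d on that between-arm contrast, and name the histology parameters it covers.
3. Report within-arm Day 0 to Day 5 change as descriptive only, with no efficacy conclusion.
4. State the order of debridement and the Day 0 punch as carried out, when compression began relative to Day 0, and where the Day 5 punch lay relative to the first.

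Both biopsies are already taken, so the cost is rewording and a small amount of analysis work. Much of the text is in the past tense. If data have already been seen, the change should be disclosed as made after the fact and the originally named tests reported beside it.

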Title: A RCT Evaluating Efficacy of Type-I Collagen Skin Substitute vs. Human Amnion Membrane in Treatment of Venous Leg Ulcers

NCT No: NCT06831760

Date: July 8, 2025

Study Aims

This randomized, controlled clinical trial aimed to compare clinical efficacy, healing outcomes, of High Purity Type-I Collagen Skin Substitute (HPTC) vs. Dehydrated Human Amnion / Chorion Membrane (dHACM) in the treatment of venous leg ulcers.

Sample Size Calculation

Standard Two-Sample Comparison of Proportions (e.g., wound closure rate)

Assuming:

- $\alpha = 0.05$ (5%)
- **Power** = 0.80 (80%)
- **Proportion of success in control (p_1)** = 0.60 (typical healing rate for dHACM)
- **Proportion of success in treatment (p_2)** = 0.90 (expected improvement with Type-I collagen)

We use the formula for comparing two proportions:

$$n = (p_1 - p_2)^2 (Z\alpha/2 + Z\beta)^2 / [p_1(1 - p_1) + p_2(1 - p_2)]$$

Where:

- $Z\alpha/2 = 1.96$ for $\alpha = 0.05$
- $Z\beta = 0.84$ for 80% power

$$n = (1.96 + 0.84)^2 \cdot [0.6(0.4) + 0.9(0.1)] / (0.9 - 0.6)^2 = 7.84 \cdot [0.24 + 0.09] / 0.09 = 7.84 \cdot 0.33 / 0.09 = 2.59 / 0.09 \approx 28.8$$

We use the formula for comparing two proportions:

$$n = \frac{(Z_{\alpha/2} + Z_{\beta})^2 \cdot [p_1(1 - p_1) + p_2(1 - p_2)]}{(p_1 - p_2)^2}$$

Where:

- $Z_{\alpha/2} = 1.96$ for $\alpha = 0.05$
- $Z_{\beta} = 0.84$ for 80% power

$$n = \frac{(1.96 + 0.84)^2 \cdot [0.6(0.4) + 0.9(0.1)]}{(0.9 - 0.6)^2} = \frac{7.84 \cdot [0.24 + 0.09]}{0.09} = \frac{7.84 \cdot 0.33}{0.09} = \frac{2.59}{0.09} \approx 28.8$$

~29 participants per group - 30 per group is statistically adequate to detect a difference from 60% to 90% healing rate with 80% power.

Randomization and Blinding: Patients were randomized 1:1 to the HPTC or dHCAM group using a computer-generated randomization sequence. Open-label design (patients and clinicians were aware of treatment allocation). Outcome assessors and statisticians were blinded.

Data Collection and Monitoring

- a. Baseline data: Demographics, medical history, ulcer characteristics.
- b. Weekly follow-ups: Wound measurements (photographic documentation), assess healing progress, pain scores, record adverse events and patient-reported outcomes.
- c. Histopathological specimens were obtained at baseline and day 5 for vascularity assessment.
- d. End-of-Study Visit (Week 6): final wound assessment, collect patient feedback on treatment experience, quality of life and scar assessment.

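### Vascular Infiltration is counted per field but scored 0–3, and the SAP names no ordinal method; analysing the count would keep power that any test on the grade gives up

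*Protocol*

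**What the plan says.** Six parameters are listed under the vascularity outcome (Protocol, Secondary Outcome Measure i, Histological Parameters Evaluated). Three matter here.

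- Parameter 1, Vascular Infiltration, is "Assessed by counting new blood vessels per High Power Field (hpf") and scored 0 to 3. The bands are fewer than 5, 5 to 10, 11 to 20 and more than 20 vessels; grade 1, for example, is "Mild infiltration (5-10 vessels/hpf").
- Parameter 3, Fibroblast Activity, combines a count of α-SMA "positive fibroblasts per HPF and assessment of fibroblast morphology". Its 0–3 levels are described in words, without count limits.
- Parameter 4, Capillary Density, is a CD31 vessel count per mm² with no grading.

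Neo-epithelialization, inflammatory response and collagen deposition are also graded 0–3. The Protocol says that Day 0 is to be compared with Day 5.

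The SAP (Data Analysis) gives Student's t-test for continuous variables and a "chi-square test for categorical variables", and adds that "A p-value <0.05 was considered statistically significant". It also promises Cohen's d for the primary histopathological parameters, without saying which these are. It does not place the 0–3 scores in either class, names no ordinal or rank method, and does not say how Day 0 enters the comparison.

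**The concern.** Cutting a count into four bands discards information. A biopsy with 11 vessels and one with 20 get the same grade, while 10 and 11 get different grades. If the grade is then tested with an unordered chi-square, the ordering is lost as well: the statistic is the same however the four grades are shuffled. With 30 patients per arm, each biopsied twice, a real difference in vessel ingrowth becomes easier to miss. Because the SAP leaves the test for the grades open, it could also be chosen after the results are seen.

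**Working it through.** **The plan's own figure.** The only power calculation is for wound closure: (1.96 + 0.84)² × [0.6 × 0.4 + 0.9 × 0.1] / (0.9 − 0.6)² = 7.84 × 0.33 / 0.09 = 28.7, against 28.8 in the SAP, which rounds the numerator to 2.59 before dividing. The SAP concludes that "30 per group is statistically adequate to detect a difference from 60% to 90% healing rate with 80% power". This reproduces, but it says nothing about histology.

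**Inputs from the documents.** 30 per arm, 1:1 allocation, two-sided 0.05, and cut-points <5, 5–10, 11–20 and >20.

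**Inputs assumed.** Count distribution, mean, spread and difference between arms, because the documents give none. Dropout is taken as zero, and only Day 5 values are compared.

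**Tests compared.**

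- t-test on the count: power depends on d√(n/2). At d = 0.74 this is 0.74 × √15 = 2.87. The normal approximation gives Φ(2.87 − 1.96) = Φ(0.91), about 82%; the t distribution gives about 80%.
- t-test or Mann-Whitney test on the 0–3 grade.
- Pearson chi-square on the 2 × 4 table, Σ(O − E)²/E, with (2 − 1)(4 − 1) = 3 df when all four grades occur.

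**Simulation 1.** Negative-binomial counts with variance m + m²/k, 6,000 trials per row. Power is in per cent; losses are in percentage points against the count t-test.

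| Means, k | Count t | Grade t | Grade chi-square | Loss, grade t | Loss, chi-square |
|---|---|---|---|---|---|
| 12 v 16, 10 | 74 | 64 | 44 | 10 | 30 |
| 12 v 16.5, 5 | 64 | 55 | 38 | 9 | 26 |
| 13 v 18, 6 | 72 | 62 | 45 | 10 | 27 |
| 8 v 11, 8 | 70 | 61 | 40 | 9 | 30 |
| 14 v 18.5, 10 | 74 | 64 | 46 | 10 | 28 |
| 16 v 22, 6 | 73 | 60 | 45 | 13 | 28 |

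In 70–98% of these simulated tables at least one expected cell count was below 5, so the chi-square approximation is also strained.

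**Simulation 2.** Rounded-normal or negative-binomial counts, control mean 6–18 and SD 3–8 per field, 8,000 trials per scenario, with the standardised difference d fixed. Loss against the count t-test, in points, as range (median):

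| d | Grade t-test | Grade Mann-Whitney | Grade chi-square |
|---|---|---|---|
| 0.50 | 4.1–15.2 (7.6) | 5.2–15.6 (8.4) | 16.2–27.4 (21.6) |
| 0.74 | 5.9–20.5 (10.2) | 6.4–21.0 (10.9) | 23.5–37.1 (28.6) |
| 0.85 | 5.0–16.8 (9.7) | 5.4–17.1 (10.2) | 21.0–34.1 (27.2) |

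At d = 0.74 the count t-test has about 80% power with normal counts and 61–75% with negative-binomial counts. Of the median chi-square loss of 28.6 points, about 10 come from the grading and the remaining 18 or so from ignoring order.

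**Very large effects (k = 6), count t-test v grade chi-square.** Means 8 v 14: 98% v 88%, loss 10. Means 10 v 18: 99.6% v 94%, loss 5.6. Means 8 v 16: 99.9% v 98%, loss 1.9.

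**The case against.** The strongest reply is that the SAP never assigns chi-square to the grades. A reader might infer that a four-level score must be a categorical variable, and so that the plan simply forfeits 25–30 points. The text does not support that. The only sentence specific to histology promises Cohen's d, a mean-and-SD measure, which points toward comparing means; on that reading the loss is typically about 10 points. This stands, and the larger figure must stay conditional. Cohen's d does not settle the matter, though: it is an effect size rather than a test, and the parameters it covers are not named.

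Three other strong readings also fail.

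- *The whole vascularity outcome is weakened.* CD31 density sits under the same outcome, is ungraded, and would naturally go to a t-test. Nothing says that Vascular Infiltration alone is the endpoint.
- *The fibroblast count is never used.* The levels refer to cellularity, which a count can inform. Numeric limits are missing, but no power loss can be computed from that.
- *Values between 10 and 11 have no grade.* Whole-number counts are fully covered, and the documents do not say that fields or readers are averaged.

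The size also rests on assumed distributions and shrinks at very large effects. The stated Day 0 to Day 5 comparison was not modelled. Finally, neither document says that raw counts are kept as data, so the remedy may cost more than a change of wording.

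**Conclusion.** The point holds as a worthwhile, inexpensive improvement to one of two vascularity measures under a secondary outcome. In every scenario examined the count had more power than the grade, whichever test was put on the grade. With 30 per arm and moderate effects, the loss is roughly 6–21 points (typically about 10) for a t-test or rank test, and roughly 23–37 (typically 25–30) if an unordered chi-square is used. The chi-square loss is 16–27 points at d = 0.50, and 10 or fewer at the very large effects tried. These figures depend on assumed count distributions and effect sizes, full follow-up and a Day 5 comparison. No loss is claimed for CD31 density or for fibroblast activity.

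**What to change.** In the SAP's Data Analysis section:

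1. Analyse Vascular Infiltration as vessels per field at Day 5, on a log or square-root scale, adjusted for the Day 0 count. State how the two pathologists' readings give one value per patient.
2. Show the 0–3 vascular grade as description only.
3. For parameters that exist only as 0–3 grades, name a rank or ordinal test in place of an unordered chi-square.
4. Where α-SMA fibroblast counts are recorded, analyse them in the same way as the vessel counts, alongside the composite grade.

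No further biopsy is needed. The cost is SAP wording and entry of the raw counts, or their retrieval from pathology records; if only grades were kept, slides might have to be re-read. Both documents describe the analysis in the past tense. If the data have already been analysed unblinded, the count analysis should be reported as post hoc.

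### Vascular Infiltration is defined by "new" vessels with no rule for identifying them and graded on plain vessel counts, and the SAP states no analysis that uses the Day 0 reading

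*Protocol*

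**What the plan says.** In the Protocol, under Histological Parameters Evaluated, item 1 (Vascular Infiltration) is "Assessed by counting new blood vessels per High Power Field (hpf" and is then graded 0 to 3. The grade labels speak of ingrowth or infiltration, but their limits are numbers of vessels without the word "new": the lowest is "Minimal vascular ingrowth (<5 vessels/hpf" and the highest "Abundant infiltration (>20 vessels/hpf".

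Four stains are listed, each with a purpose: "Hematoxylin and Eosin (H&E) for general morphology", "Masson's Trichrome for collagen assessment", "CD31 immunohistochemistry for capillary density evaluation" and (alpha-) "SMA immunohistochemistry for fibroblast activity". Items 3, 4 and 6 name the stain they use. Item 1 names none.

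On timing, secondary outcome i states: "Vascularity assessment will be done using biopsy on Day 0 of application to be compared with Day 5 after application". The first punch is taken before any product is applied, and each punch includes tissue from the ulcer margin as well as the bed. Item 4 (Capillary Density) separately counts CD31 vessels per square millimetre, without the word "new".

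The SAP's Data Analysis section gives t-tests and chi-square tests between groups, Kaplan-Meier for healing time, and Cohen's d for histology. It does not mention the Day 0 histology values.

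**The concern.** The definition and the scale of item 1 name different quantities, and nothing in the text connects them. No morphology, location, marker or subtraction of the Day 0 count is given for calling a vessel new. At Day 0 the natural meaning, formed since application, is not available. A reader could then record zero, record every vessel, or record vessels that look immature, and could do something different on Day 5.

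This is the first-listed parameter of the first secondary outcome, and it carries that outcome's name. If the two days are read by different rules, Day 0 is not a baseline for Day 5, and an apparent rise may reflect the change of rule. If both days are read by one rule but Day 0 is left out of the analysis, a measurement that required an extra biopsy contributes nothing to the comparison between arms.

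**Working it through.** There is no stated figure to reproduce. The check has three parts.

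**1. The text side by side.**

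| Element | What is counted |
|---|---|
| Item 1 definition | new vessels per field |
| Item 1 grade limits (<5, 5-10, 11-20, >20) | vessels per field |
| Stain assigned to item 1 | none |
| Rule for "new" | none |
| Day 0 sample | taken before application |
| Item 4 | CD31 vessels per mm², no "new" |
| SAP analysis using Day 0 histology | none stated |

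**2. How far the word can move a grade.** The cut-points are the Protocol's; the background counts are assumptions, because the documents give no vessel counts. Compare the grade of the new vessels alone with the grade of new plus background.

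- 0 new (grade 0): 0 + 5 = 5, grade 1; 0 + 15 = 15, grade 2; 0 + 21 = 21, grade 3.
- 3 new (grade 0): 3 + 5 = 8, grade 1; 3 + 10 = 13, grade 2; 3 + 21 = 24, grade 3.
- 8 new (grade 1): 8 + 5 = 13, grade 2; 8 + 15 = 23, grade 3.

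So the choice can move a grade by one to three steps. With assumed background means (SDs) of 5 (2), 8 (3) and 12 (5) vessels per field and no new growth at all, an all-vessel count puts 57%, 86% and 93% of Day 5 biopsies at grade 1 or above. The first figure is 50% if the average count is not rounded to whole vessels. Read by the same rule, Day 0 would show the same vessels and no rise. The artefact arises only when the two days are read differently.

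**3. What adjusting for Day 0 is worth.** This is a simulation with 30 per arm, the background distributions above, Poisson counts averaged over 5 fields, and new growth gamma-distributed (shape 4) with mean 7 in one arm and 4 in the other. All vessels are counted by one rule on both days. The Day 5 counts are compared by t-test, or by ANCOVA (Day 5 count = intercept + arm + slope × Day 0 count). The correlation is that of a patient's background density between the two biopsies.

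| Analysis | 5 (2) | 8 (3) | 12 (5) |
|---|---|---|---|
| Day 5 alone | 0.87 | 0.73 | 0.48 |
| ANCOVA, correlation 0 | 0.86 | 0.73 | 0.47 |
| ANCOVA, correlation 0.5 | 0.88 | 0.76 | 0.56 |
| ANCOVA, correlation 0.7 | 0.90 | 0.81 | 0.60 |
| ANCOVA, correlation 1 | 0.94 | 0.91 | 0.88 |

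At correlation 0.5 the gains are 0.88 − 0.87 = 0.01, 0.76 − 0.73 = 0.03 and 0.56 − 0.48 = 0.08. At correlation 0 the loss is at most 0.01. Each entry carries a point or two of simulation error. The test is on the count per field, not on the 0-3 grade.

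**The case against.** The strongest reply is that this is a drafting gap with limited reach. Item 1 is one of six histological parameters within one secondary outcome. The two pathologists do not know the arm and would apply whatever rule they use to both arms, so the ambiguity does not by itself favour either product. Kappa is planned and would reveal disagreement between readers. Item 4 already supplies a vessel count without the word "new". All of that stands. It limits the consequence to interpretation, reproducibility and precision. It does not say what item 1 measures: kappa reports disagreement without resolving it, and blinding does not supply a definition.

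The SAP's t-test could also have been meant for the change from Day 0. The text does not exclude that, but it does not say so.

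Three stronger readings are tempting, and the documents do not support them.

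- A reader might infer that none of the four stains can distinguish new vessels. The Protocol shows only that no stain is assigned that task. It does not rule out judging morphology on H&E or reading the CD31 and alpha-SMA sections together.
- A reader might infer that the score is therefore a total count. The text leaves the quantity undefined; it may be a total count.
- A reader might infer that Day 0 must be either zero or the total. "New" could mean immature vessels in the bed, which an ulcer open for more than 4 weeks might contain before treatment. That reading is possible, but nowhere stated.

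**Conclusion.** The point holds in limited form. Item 1 does not fix what is counted, the Day 0 and Day 5 readings may differ in kind, and the promised comparison of the two days has no stated analysis. These conclusions rest on the text alone.

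The sizes rest on assumed vessel counts. A grade can shift by one to three steps according to how "new" is read. The gain in power from adjusting for Day 0 runs from nothing (or a loss of about a point) at correlation 0, through about 1 to 8 points at 0.5, to 0.94, 0.91 and 0.88 at correlation 1. The last row should not be taken as the expected benefit: the two punches are different pieces of tissue, so identical background density is a best case.

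Nor do the documents support a forecast that reader agreement will collapse. If one reader calls 20% of background vessels new and the other 60%, simulated kappa is 0.39, 0.19 and 0.05 in the three settings; at 35% against 45% it is 0.83, 0.77 and 0.71. The result depends almost entirely on the pair of readers assumed.

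The case for the change is that it uses data already collected and costs almost nothing in power if the correlation turns out to be low.

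**What to change.** In the Protocol, score item 1 as vessels per high-power field, with one written counting and field-selection rule applied identically on Day 0 and Day 5. The rule must be the same; the fields cannot be, because the Day 0 tissue has been removed. Reword the grade labels, and any claim based on them, to vessel number in place of new ingrowth. Keep the count itself as well as the grade.

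In the SAP, state that arms are compared on the Day 5 count adjusted for the patient's own Day 0 count (ANCOVA). Say openly that item 1 then largely overlaps with item 4, and apply the same Day 0 adjustment to item 4.

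No further patients, biopsies or stains are needed. There are two costs. The trial can no longer claim to have counted new vessels directly. And since the Protocol describes the readings in the past tense, slides already read under another rule would have to be re-read, or the rule actually used disclosed and the claim limited accordingly.
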